## 8.8 Other Response Data Analysis

Tumor assessment at baseline, including sum of target lesion diameters, number of subjects with target lesions and non-target lesions will be summarized in the All Treated Population for solid tumors and lymphoma, respectively, if data warrants.

For solid tumors response assessment based on iRECIST, lesion assessment including target lesion measurements and sum of diameters, non-target lesions and new lesions will be presented in data listings.

For lymphoma response assessment based on RECIL 2017, lesion assessment including target lesion measurements and sum of diameters, non-target lesions and new lesions will be presented in data listings.

## 8.9 Progression Free Survival

The PFS data analysis will be based on iRECIST and RECIST 1.1 for solid tumors and RECIL 2017 for lymphoma using All Treated Population.

### 8.9.1 PFS based on iRECIST for Solid Tumors

PFS based on iRECIST is defined as time from the first day of treatment to the first documented disease progression (iUPD) that is subsequently confirmed or death, whichever occurs first. If iUPD occurs but is disregarded because of later iSD, iPR or iCR, that iUPD date should not be used as the progression event for PFS. If iUPD is not confirmed and there is no subsequent iSD, iPR or iCR, then the iUPD date should still be used as progression event for PFS in the following scenarios: if the subjects stop study treatment because they were not judged to be clinically stable, or no further response assessments are done; the next timepoint responses are all iUPD, and iCPD never occurs; or the subject dies from their cancer.

Subjects who have not progressed at the time of analysis will be censored at the time of the latest date of assessment from their last evaluable iRECIST assessment. The censoring guidance and the date of PD/death or censoring are given in the Table 5 below.

**Table 5. Summary of Censoring Guidelines for PFS based on iRECIST**

Situation	Date of PD/Death or Censoring	PFS Outcome
Documented iCPD or death	Date of the initial iUPD that is confirmed or death, whichever comes first	Event (unless the censoring rule specified below)
iUPD and if iUPD is not confirmed and there is no subsequent iSD, iPR or iCR 	Date of the last iUPD	Event (unless the censoring rule specified below)
Death or iUPD immediately after $\geq 2$ consecutive missed or non-evaluable disease assessments  as per the protocol specified assessment schedule	Date of last evaluable disease assessment prior to missed or non-evaluable assessments, or the first dose of investigational product, whichever occurred last	Censored
No iCPD or death at time of analysis or lost to follow-up	Date of last evaluable disease assessment	Censored
No tumor assessment at baseline OR No tumor assessment post-first dose, and no death prior to second scheduled post-baseline disease assessment	Date of first dose	Censored

 If iUPD is not confirmed and there is no subsequent iSD, iPR or iCR, then the iUPD date should still be used as progression event for PFS in the following scenarios: if the subjects stop study treatment because they were not judged to be clinically stable, or no further response assessments are done; the next timepoint responses are all iUPD, and iCPD never occurs; or the subject dies from their cancer.

 Two or more consecutive assessments is defined as  $\geq 16+1$  weeks for the first 6 months or  $\geq 24+1$  weeks for 6-24 months (two disease assessments as per protocol plus a one week visit window to allow for a late assessment) after the last evaluable post-baseline disease assessment. If a subject has two or more consecutive missed or non-evaluable assessments followed by an assessment showing no radiologic disease progression, then the assumption will be that the subject did not progress during the missed or non-evaluable assessments.

The median and quartiles of PFS and their 95% CIs will be assessed using the Kaplan-Meier method and Brookmeyer and Crowley (1982) method, respectively. The proportion of subjects

that are progression free and alive at 12, 24, 48, 72, 96 weeks and other timepoints of interest and associated 95% CI will be estimated using the Kaplan-Meier method.

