8.1.2 Response and Stable Disease Duration

Response duration will be measured from the time measurement criteria for iCR/iPR (whichever is first recorded) are first met until the first date that recurrent or progressive disease is objectively documented, taking as reference the smallest measurements recorded on study (including baseline). Stable disease (SD) duration will be measured from the time of start of treatment until

the criteria for progression are met, taking as reference the smallest sum on study (including baseline).

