When using iRECIST, the definitions of measurable and non-measurable lesions still follow RECIST 1.1. The principles used to establish an objective tumor response when using iRECIST are largely unchanged from RECIST 1.1, however, responses assigned using iRECIST have a prefix of “i” (e.g., “immune” complete response [iCR]) to differentiate them from responses assigned using RECIST 1.1.

The major change is the concept of resetting the bar if RECIST 1.1 progression is followed at the next assessment by tumor shrinkage. This adaptation accounts for instances where an increase in tumor burden, or the appearance of new lesions, does not reflect true tumor progression. Therefore, iRECIST requires confirmation of progression.

Confirming Progression: iRECIST requires the confirmation of progression and uses the terms iUPD (unconfirmed progression) and iCPD (confirmed progression). Confirmatory scans should be performed at least 4 weeks after iUPD. iCPD is confirmed if further increase in tumor burden, compared to the last assessment, is seen as evidenced by one or more of the following criteria:

- Continued increase in tumor burden (from iUPD) where RECIST 1.1 definitions of progression had been met (from nadir) in target, non-target disease or new lesions.
 - Progression in target disease worsens with an increase of at least 5 mm in the absolute value of the sum
 - Continued unequivocal progression in non-target disease with an increase in tumor burden
 - Increase in size of previously identified new lesion (s) (an increase of at least 5 mm in the absolute value of the sum of those considered to be target new lesions) or additional new lesions
- RECIST 1.1 criteria are met in lesions types (target or non-target or new lesions) where progression was not previously identified, including the appearance of additional new lesions.
- If iUPD is not confirmed at the next assessment, then the appropriate response will be assigned (iUPD if the criteria are still met, but no worsening, or iSD, iPR or iCR if those criteria are met compared to baseline).

New Lesions: New lesions should be assessed and measured as they appear using RECIST 1.1 criteria (maximum of 5 lesions, no more than 2 per site, at least 10 mm in long axis (or 15 mm in short axis for nodal lesions) and recorded as New Lesions-Target (NLT) and New Lesion-Non-Target (NLNT) to allow clear differentiation from baseline target and non-target lesions.

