New lesions may either meet the criteria of NLT or NLNT to drive iUPD (or iCPD). However, the measurements of target lesions should NOT be included in the sum of measures of original target lesions identified at baseline. Rather, these measurements will be collected on a separate table in the eCRF.

Progressive disease is confirmed in the New Lesion category if the next imaging assessment, conducted at least 4 weeks (but not more than 8 weeks) after iUPD confirms further progression from iUPD with either an increase of at least 5 mm in the absolute value of the sum of NLT OR an increase (but not necessarily unequivocal increase) in the size of NLNT lesions OR the appearance of additional new lesions.

iRECIST Time Point Response Table

Target Lesions	Non-Target Lesions	New Lesions	Time Point Response (TPR)	
			No prior iUPD	Prior iUPD
iCR	iCR	No	iCR	iCR
iCR	Non-iCR/Non-iUPD	No	iPR	iPR
iPR	Non-iCR/Non-iUPD	No	iPR	iPR
iSD	Non-iCR/Non-iUPD	No	iSD	iSD
iUPD with no change OR decrease from last TP	iUPD with no change OR decrease from last TP	Yes	NA	NLs confirms iCPD if NL were previously identified and increase in size (≥ 5 mm in SOM for NLT or any increase for NLNT) or number. If no change in NLs (size or number) from last TP, remains iUPD
iSD	iUPD	No	iUPD	Remains iUPD unless iCPD confirmed based in further increase in size of NT disease (need not meet RECIST 1.1 criteria for unequivocal PD)
iUPD	iUPD	No	iUPD	Remains iUPD unless iCPD confirmed based on: further increase in SOM of at least 5 mm, otherwise remains iUPD
iUPD	iUPD	No	iUPD	Remains iUPD unless iCPD confirmed based on further increase in: previously identified T lesion iUPD SOM ≥ 5 mm and/or NT lesion iUPD (prior assessment need not be unequivocal PD)

Target Lesions	Non-Target Lesions	New Lesions	Time Point Response (TPR)	
			No prior iUPD	Prior iUPD
iUPD	iUPD	Yes	iUPD	Remains iUPD unless iCPD confirmed based on further increase in: 
 • previously identified T lesion iUPD SOM ≥ 5 mm and/ • previously identified NT lesion iUPD (prior assessment need not be unequivocal PD) • size or number of new lesions previously identified
Non-iUPD/PD	Non-iUPD/PD	Yes	iUPD	Remains iUPD unless iCPD confirmed based on: 
 • increase in size or number of new lesions previously identified

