**Table 6. Summary of Censoring Guidelines for PFS based on RECIST1.1**

Situation	Date of PD/Death or Censoring	PFS Outcome
Documented PD or death	Date of the first PD or death, whichever comes first	Event (unless the censoring rule specified below)
Death or PD immediately after $\geq 2$ consecutive missed or non-evaluable disease assessments  as per the protocol specified assessment schedule	Date of last evaluable disease assessment prior to missed or non-evaluable assessments, or the first dose of investigational product, whichever occurred last	Censored
No PD or death at time of analysis or lost to follow-up	Date of last evaluable disease assessment	Censored
No tumor assessment at baseline OR No tumor assessment post-first dose, and no death prior to second scheduled post-baseline disease assessment	Date of first dose	Censored

 Two or more consecutive assessments is defined as  $\geq 16+1$  weeks for the first 6 months or  $\geq 24+1$  weeks for 6-24 months (two disease assessments as per protocol plus a one week visit window to allow for a late assessment) after the last evaluable post-baseline disease assessment. If a subject has two or more consecutive missed or non-evaluable assessments followed by an assessment showing no radiologic disease progression, then the assumption will be that the subject did not progress during the missed or non-evaluable assessments.

The median and quartiles of PFS and their 95% CIs will be assessed using the Kaplan-Meier method and Brookmeyer and Crowley (1982) method, respectively. The proportion of subjects that are progression free and alive at 12, 24, 48, 72, 96 weeks and other timepoints of interest and associated 95% CI will be estimated using the Kaplan-Meier method.

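### SAP Table 5 dates a never-confirmed iUPD at the last scan that shows it, so read literally iRECIST PFS lengthens with each further scan

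*SAP*

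**What the plan says.** SAP 8.9.1 defines iRECIST PFS by the first iUPD that is later confirmed, or death. It discards an iUPD that is followed by iSD, iPR or iCR. It then keeps certain unconfirmed, unreset iUPDs as events: "then the iUPD date should still be used as progression event for PFS". One of the listed scenarios is that "the next timepoint responses are all iUPD, and iCPD never occurs".

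Table 5 turns this into dates:

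- Row 1, confirmed progression or death: "Date of the initial iUPD that is confirmed or death, whichever comes first".
- Row 2, iUPD not confirmed and with no later iSD, iPR or iCR: "Date of the last iUPD". Footnote 1 to this row repeats the all-iUPD scenario.

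Elsewhere the first date is used. Table 6, for RECIST 1.1 PFS, has "Date of the first PD or death, whichever comes first", and RECIL PFS (SAP 8.9.3) follows the same guidance. Protocol 8.1.2 measures response duration "until the first date that recurrent or progressive disease is objectively documented". SAP Section 12, which lists departures from the protocol analyses, does not mention a last-date rule.

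**The concern.** Under Protocol 16.6.3, a repeat scan that does not confirm progression is classed as "iUPD if the criteria are still met, but no worsening". In an unbroken run of iUPD, the progression criteria were therefore met at the first scan of the run and at every later one. Dating the event at the last scan makes PFS depend on how many scans were done after the criteria were first met. Compared with first-iUPD dating, the shift can only lengthen PFS.

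Repeat scans are foreseeable. SAP Section 8 continues imaging until progression is confirmed and asks for a confirmatory assessment after an unconfirmed progression. Protocol 8.3 allows treatment past initial progression.

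Figure 14.2.5 plots iRECIST and RECIST 1.1 PFS together. A reader will take the gap between the curves to be subjects whose early progression was reset. Part of it could instead come from this dating rule.

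**Working it through.** The plan gives no figure of its own here, so the check applies each rule to the same response sequences.

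**Inputs**
- Time to event = event date − first dose date + 1, and months = days / 30.4375 to one decimal (SAP 5.2.3).
- Scans every 8 weeks through week 24, every 12 weeks to year 2, then every 6 months (SAP Section 8).
- Confirmatory scan at least 4 weeks after iUPD (Protocol 16.6.3). For new lesions it is "conducted at least 4 weeks (but not more than 8 weeks) after iUPD".
- RECIST 1.1 PD is derived as iUPD or iCPD (SAP 8.2.1), so the first iUPD is the first PD.
- Assumption: scans fall exactly on schedule, so week w is study day 7w + 1. Week 8 gives 7 × 8 + 1 = 57, which matches the day shown for C3D1 in the Schedule of Assessments.

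**Conversions:** 57/30.4375 = 1.9; 85/30.4375 = 2.8; 113/30.4375 = 3.7; 169/30.4375 = 5.6; 253/30.4375 = 8.3 months.

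| iUPD at weeks (never confirmed) | First iUPD of final run, day (months) | Last iUPD, day (months) | Shift, days | RECIST 1.1, day |
|---|---|---|---|---|
| 8 only | 57 (1.9) | 57 (1.9) | 0 | 57 |
| 8, and 12 (4-week repeat scan) | 57 (1.9) | 85 (2.8) | 28 | 57 |
| 8, 16 | 57 (1.9) | 113 (3.7) | 56 | 57 |
| 8, 16, 24 | 57 (1.9) | 169 (5.6) | 112 | 57 |
| 24, 36 | 169 (5.6) | 253 (8.3) | 84 | 169 |
| 8, then iSD at 16, then iUPD at 24, 36 | 169 (5.6) | 253 (8.3) | 84 | 57 |

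**Contrast inside Table 5.** iUPD at weeks 8 and 16 followed by iCPD at week 24 is dated day 57 by row 1. iUPD at weeks 8, 16 and 24 without iCPD is dated day 169 by row 2. Both subjects first met the criteria at week 8 and neither returned to iSD or better, yet their dates differ by 169 − 57 = 112 days.

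**What the comparison with RECIST 1.1 would show.** In the last row of the table, the move from day 57 to day 169 (112 days) is the genuine effect of the reset. The further 84 days to day 253 come only from the word *last*.

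**Planned 12-week PFS estimate.** 12 × 7 = 84 days. A subject with iUPD at weeks 8 and 16 has an event before day 84 under first-date dating (57 < 84) and is progression-free at day 84 under row 2 (113 > 84). With 15 subjects and no earlier censoring, each such subject adds 1/15 = 6.7 percentage points. In a pooled group of 48 (Schedule 1 escalation plus pharmacodynamic cohorts) it would be 1/48 = 2.1 points.

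**The case against.** Several points can be made for the plan.

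- *Last iUPD* may have been meant as the iUPD that remains after any reset, and footnote 1 can be read with the index iUPD in mind. That intent is plausible, but the cell does not state it. SAP 8.9.1 already discards reset iUPDs, so the word is not needed for that purpose, and the footnote brings all-iUPD runs into the row.
- The first-date rules elsewhere cover other situations: confirmed progression, RECIST 1.1, and response duration. This is true. The SAP has no explicit first-date rule for never-confirmed iUPD, so the case rests on inconsistency with neighbouring rules.
- Without row 2, such a subject would be censored at the last evaluable assessment, normally the same scan. Row 2 then turns a censoring into an event, and last-date dating could be deliberate. If so, the SAP should say so and justify it; it does neither.
- Runs may be uncommon. Small further growth, or a further new lesion, converts iUPD to iCPD, and treatment past progression has conditions. This stands: the documents support that runs can occur, not how often. The weeks 24 and 36 example also needs no confirmatory scan in between.
- A subject with unconfirmed iUPD who dies of cancer fits both row 1 and row 2. This also stands, and changing the date in row 2 alone does not settle it.

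**Conclusion.** The concern holds as a matter of text. Read literally, row 2 gives a later event date for any subject with two or more consecutive unconfirmed, unreset iUPDs. The delay per extra scan is as little as 4 weeks with a confirmatory scan, otherwise 8 weeks through week 24 and 12 weeks from then to year 2, assuming on-schedule scans. The number of affected subjects cannot be derived from the documents, so the effect on the median or on any landmark rate is not known.

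The reach is limited. PFS is exploratory and descriptive. RECIST 1.1 PFS, ORR, CBR and the primary safety and MTD analyses are untouched. iRECIST DOR is involved only through SAP 8.6, which defines progression as confirmed but then takes its event dates from 8.9.1. The rule should be corrected because it works in one direction only, affects a scenario the SAP itself names, and blurs a planned comparison.

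**What to change.** In Table 5 row 2, replace the date with: *Date of the first iUPD in the final unbroken run of iUPD (no intervening iSD, iPR or iCR)*. Use the same words in SAP 8.9.1 and footnote 1. An earlier iUPD that was reset is still ignored.

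In SAP 8.6, state whether a never-confirmed iUPD run is a DOR event and, if so, that the same date applies. While the table is open, say which row governs when a subject with unconfirmed iUPD dies.

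The cost is one table cell, matching words in two places, a sentence each on DOR and death, and a small programming change. The row 2 date change moves iRECIST PFS dates earlier only for subjects with two or more consecutive unreset, unconfirmed iUPDs.

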Categorical variables will be summarized by counts and by percentages of subjects in the corresponding categories. Percentages are routinely based on the total number of the specified population N if not otherwise specified. For frequency counts, categories whose counts are zero will be displayed for the sake of completeness. For example, if none of the subjects discontinue due to “lost to follow-up,” this reason will be included in the table with a count of 0. Categories with zero counts will not have zero percentages displayed.

All confidence intervals (CIs) will be constructed at the 95% confidence level, unless specified otherwise.

All analyses and tabulations will be performed using SAS® v9.4 or above.

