## 8.6 Duration to Response

DOR based on iRECIST is defined as time from the date of initial response (iCR or iPR confirmed at least 28 days later) to the date of first documented disease progression that is confirmed or death, whichever occurs first. Only subjects who have achieved objective response (confirmed iCR or confirmed iPR) will be evaluated for DOR. The censoring guidance and the date of PD/death or censoring are same as that for PFS in Section 8.9.1.

DOR based on RECIST 1.1 is defined as time from the date of the first CR or PR (confirmed at least 28 days later) to the date of first documented disease progression (confirmed or not) or death, whichever occurs first. Only subjects who have achieved objective response (confirmed CR or confirmed PR) will be evaluated for DOR. If a disease progression does not occur, DOR will be censored as of the date of their last evaluable disease assessment. The censoring guidance and the date of PD/death or censoring are same as that for PFS in Section 8.9.2.

DOR based on RECIL 2017 is defined as time from the date of the first CR or PR to the date of first documented disease progression (confirmed or not) or death, whichever occurs first. Only

subjects who have achieved objective response (CR or PR) will be evaluated for DOR. If a disease progression does not occur, DOR will be censored as of the date of their last evaluable disease assessment. The censoring guidance and the date of PD/death or censoring are same as that for PFS in Section 8.9.3.

If data warrants, the median and quartiles of DOR and their 95% CIs will be assessed using the Kaplan-Meier method and Brookmeyer and Crowley (1982) method, respectively, and the DOR will be presented in a data listing.

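### SAP Table 5 counts a never-confirmed iUPD as a PFS event in row 2 but, read literally, censors the same living subject in row 4, contradicting SAP 8.9.1

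*SAP*

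**What the plan says.** SAP 8.9.1 defines iRECIST PFS by the first iUPD that is later confirmed, or death. It then adds an exception. If an iUPD is neither confirmed nor followed by iSD, iPR or iCR, "then the iUPD date should still be used as progression event for PFS in the following scenarios": treatment stopped because the subject was not judged clinically stable, no further response assessment, later responses all iUPD, or death from the cancer. Footnote 1 of Table 5 repeats this. The narrative censors only subjects who have not progressed.

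The relevant Table 5 rows, numbered from the top, are:

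- Row 1: documented iCPD or death. Event.
- Row 2: "iUPD and if iUPD is not confirmed and there is no subsequent iSD, iPR or iCR". Event, dated "Date of the last iUPD".
- Row 3: death or iUPD directly after two or more missed or non-evaluable assessments. Censored.
- Row 4: "No iCPD or death at time of analysis or lost to follow-up". Censored, dated "Date of last evaluable disease assessment".
- Row 5: no baseline or no post-dose tumor assessment. Censored.

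The outcome cell of rows 1 and 2 reads "Event (unless the censoring rule specified below"; it does not say which of the rows below it means.

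SAP 8.6 runs iRECIST DOR "to the date of first documented disease progression that is confirmed or death, whichever occurs first", then imports the censoring guidance of 8.9.1.

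**The concern.** The rows are not mutually exclusive, and the tie-break favors censoring. The subjects caught are those who progress, stop, have no confirmatory scan and are alive at analysis. They would leave the risk set at the moment of progression without counting as events. That is informative censoring, and it lengthens PFS.

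Such subjects are foreseeable. Protocol 3.12 specifies continued disease assessment for those who stop treatment for reasons other than progression. Protocol 8.3 allows treatment past first progression only without clinical symptoms of progression. SAP 8.1.3 keeps iUPD as a best-response category.

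Median PFS and week-24 PFS are planned outputs, and SAP Figures 14.2.4 and 14.2.5 show iRECIST with RECIST 1.1. A coding artefact could therefore look like a gain under iRECIST. Two programmers could also follow the same table and report different event counts.

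**Working it through.** **Overlap of the rows.** The plan gives no figure to reproduce, so the check starts with logic. Take the eight combinations of iCPD (yes/no), death (yes/no) and unconfirmed iUPD with no later iSD/iPR/iCR (yes/no), and pass them through rows 1, 2 and 4.

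- Any profile with iCPD or death fails row 4.
- No iCPD, no death, no unconfirmed iUPD: row 4 only. Correctly censored.
- No iCPD, no death, unconfirmed iUPD: rows 2 and 4 both apply.

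Exactly one of the eight conflicts. Example: iUPD at week 8, treatment stopped as not clinically stable, no further scan, alive at analysis. Row 2 gives an event at week 8. Row 4 gives censoring at the last evaluable assessment, which is that same scan. The date is unchanged; only the status flips.

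**Comparison with Table 6.** The matching RECIST 1.1 row is written in terms of PD, and SAP 8.2.1 maps both iUPD and iCPD to PD. A subject with PD can never meet it, so Table 6 has no such overlap. Table 5 uses iCPD in that place.

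**Size if no affected subject dies.** Assumed inputs, not in the documents: exponential progression with a 3-month median (91.3 days), and a share f of progressions left unconfirmed. From the documents: scans at weeks 8, 16 and 24.

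Progression probability per 8-week interval: h = 1 − 2^(−56/91.3) = 0.346.

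Week-24 PFS with every iUPD counted: (1 − h)^3 = 0.654^3 = 28%.

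Week-24 PFS with unconfirmed iUPDs censored: (1 − h(1 − f))^3.

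- f = 0.3: 0.758^3 = 43%
- f = 0.5: 0.827^3 = 57%
- f = 0.7: 0.896^3 = 72%

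Simulation on the protocol scan days agrees to within a point.

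**Size allowing for deaths.** Row 4 excludes anyone who has died, so only the share s of affected subjects still alive at analysis is miscoded, and f is replaced by f × s. Further assumptions: iUPD at day 113 (week 16), data cut-off uniform over days 200-800, exponential post-progression survival with rate λ, deaths counted as events at the iUPD date per footnote 1. Then

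s = [exp(−87λ) − exp(−687λ)] / (600λ).

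- Median survival 4 months: λ = 0.693/(4 × 30.44) = 0.00569, s = 0.17
- Median survival 9 months: λ = 0.693/(9 × 30.44) = 0.00253, s = 0.41

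| f | Survival median | f × s | Week-24 PFS | Excess over 28% |
|---|---|---|---|---|
| 0.3 | 4 months | 0.05 | 30% | 2.4 points |
| 0.3 | 9 months | 0.12 | 34% | 6 points |
| 0.7 | 4 months | 0.12 | 34% | 6 points |
| 0.7 | 9 months | 0.29 | 43% | 15 points |

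Simulation of the same set-up gives 30-34% at f = 0.3 and about 34-43% at f = 0.7. At f = 0.3 the median stays at 113 days.

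**The case against.** The strongest reply is that the intent is plain. SAP 8.9.1 and footnote 1 both say event, row 2 exists only for this case, and letting row 4 override it would leave row 2 with no effect in living subjects. Table 6 carries the same exception clause, and there it cannot point to the no-progression row. The clause was therefore probably meant for the missed-assessment and no-assessment rows. This stands as a reading of intent. It does not repair the table, which a programmer following it literally would code as censored.

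The consequence is also limited. PFS and DOR are exploratory in Protocol Table 4, and the SAP plans estimates with confidence intervals, not tests. RECIST 1.1 PFS, which counts every iUPD as PD, is reported alongside with per-subject listings, so a miscoded subject could be noticed. Scans are planned until progression is confirmed, so the share left unconfirmed may be small. All of this stands, and it bounds the importance of the point.

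A reader might infer more than the documents support in two places:

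- **iUPD at week 8, no further scans, death from cancer at week 30.** The 22-week gap exceeds the 17-week threshold of footnote 2 (2 × 8 + 1), so row 3 might seem to censor this subject. But footnote 1 names death from the cancer and makes the iUPD date the event, and that iUPD follows no missed scan. What remains is a literal ambiguity that Table 6 shares.
- **SAP 8.6 as a separate contradiction.** It follows the pattern of 8.9.1: a general definition requiring confirmation, then imported guidance with its exceptions. DOR is affected only through Table 5.

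**Conclusion.** The point holds for one profile: alive at analysis, no iCPD, and a never-confirmed iUPD with no later iSD, iPR or iCR. For that subject Table 5 as written gives the opposite status to SAP 8.9.1. The direction of bias is upward for iRECIST PFS, and for iRECIST DOR where it inherits the table.

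The documents give neither the share of unconfirmed progressions nor post-progression survival, so the size is not known. Under the assumptions above, week-24 PFS is overstated by roughly 3 to 15 points. A reader might take the 43-72% figures as the likely effect; they apply only if no affected subject dies before analysis.

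No primary or secondary result depends on this. It is still worth correcting, because a stated rule gives a wrong result and the repair is small.

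**What to change.** Four wording changes in the SAP:

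1. Reword the row 4 situation to: *No iCPD, no unconfirmed iUPD counted as an event under row 2/footnote 1, and no death*. Keep the lost-to-follow-up case under the same condition.
2. State in rows 1 and 2 that the exception refers to the missed-assessment and no-assessment rows (3 and 5).
3. State that row 3 is applied to the earliest event, so a death after an iUPD already counted as an event does not trigger it.
4. In 8.6, end iRECIST DOR at a progression event as defined in Table 5, or death.

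The cost is SAP wording and a programming check on subjects whose last response is an unconfirmed iUPD. No planned figure or data collection changes. It should be settled before database freeze, since SAP Section 1 says all analysis decisions are made by then.
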